Hypotheses: The effects of infant age of egg introduction and frequency of egg intake will vary by the child outcome of interest (**Hypothesis 1**). We predict a non-linear association between age of egg introduction and the average probability of multiple child outcomes (i.e., stunting, underweight, obesity, high risk of metabolic syndrome, food allergy, and cognitive delay), with the optimal age being a time point that falls between 6-12 months (**Hypothesis 2**). We also predict a non-linear association between frequency of infant egg intake and the average probability of multiple child outcomes, with the optimal frequency being 2-4 times per week (**Hypothesis 3**).

3) Project Design:

Sample/Data. We propose a 2-year study to examine the extent to which two important aspects of infant egg consumption (i.e., age of introduction and frequency of intake) influence physical growth, obesity, cardio-metabolic health, risk of food allergy, and cognition development in mid-childhood and adolescence. Guided by a life course framework (**Figure 1**), we will use existing secondary data from two US longitudinal birth cohorts that tracked mother-child dyads from pregnancy to adolescence: 1) **Project Viva** (1999-present, N=2,128 newborns) that followed children at delivery, 6 months (m), 1 year (y), 2 y, 3 y, 4 y, 5 y, 6 y, 7 y, 8 y, 9 y, 10 y, 11 y, 12-13 y, 14 y, and 15 y of child age,³⁷ and 2) **Infant Feeding Practices Study II** (IFPS II, 2005-2012, N=3,033 newborns) that followed children at neonatal (1 m), 2 m, 3 m, 4 m, 5 m, 6 m, 7 m, 9 m, 10 m, 12 m, and 6 y of child age.^{38,39} The PI has access to both datasets, and has 3 publications on infant nutrition, early childhood diet, growth, and obesity using Project Viva^{40,41} and IFPS II⁴² data since 2014. These two studies have a similar study design and complementary measures of child outcomes, which provide a unique opportunity for comprehensive analysis on the health effects of infant egg consumption and also external replication of findings.

Exposure measures (infant egg consumption). We will focus on age of introduction and frequency of intake as the key exposure measures of infant egg consumption, because evidence

Infant Egg Consumption | Child Health and Cognition | Clinical Guidelines

Figure 1. Conceptual framework on effects of infant egg consumption

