supports their potential influences on child health and development⁴³. We recognize that other aspects of infant egg consumption such as different egg fractions (i.e., white vs yolk⁴⁴) may also influence child outcomes but they were not collected in Project Viva or IFPS II.

Age of egg introduction. At **Project Viva** visits, the age of infant egg introduction was asked at 6-m and 12-m using the same question - “How old was your baby when you first fed him/her eggs”. In the **IFPS II**, mothers reported their infant’s intake of 18 types of foods in the past 7 days through monthly surveys from 2-12 m of infant ages. The question used for infant food intake was - “In the past 7 days, how often was your baby fed each food listed below? Include feedings by everyone who feeds the baby and include snacks and night-time feedings.” “Eggs” were one of the 18 types of foods. Accordingly, we will derive the infant age of egg introduction from IFPS II mothers’ monthly responses to infant egg consumption. Our previous analysis on infant dietary patterns showed that 1.7% and 63.0% of IFPS II infants had been introduced eggs by 6 m and 12 m of age, respectively⁴².

Frequency of egg intake. At the 2-y survey in **Project Viva**, the frequency of infant egg intake in the past month was obtained from the mothers’ response to the question - “Please check the box that best represents how often your child eats each of the foods listed, on average, in the past month”. One of the food items for this question was “Whole eggs”. Response options for the frequency of consuming “Whole eggs” included “never”, “<once/week”, “once/week”, “2–4 times/week”, “nearly daily or daily”, and “≥2 times/day”.

The same question was asked again at surveys at 3 y and 7 y. As mentioned above, mothers in the IFPS II reported their infant's intake of eggs in the past 7 days through the monthly surveys from 2-12 m of infant ages. Infant egg intake was reported as the number of feedings per day or per week. Our analysis on infant dietary patterns showed the mean egg intake among IFPS II infants was 0.01 (SD, 0.10) and 0.27 (SD, 0.37) serving/week at 6 m and 12 m, respectively⁴².

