Child outcome measures. We will focus on child physical growth, obesity, cardio-metabolic health, risk of food allergy, and cognition development (**Figure 1**). These child outcomes were chosen because they 1) may be influenced by infant egg consumption (see '**Background**'), 2) are clinically important, and 3) were measured in Project Viva and/or IFPS II.

Physical growth. In Project Viva, birth weight was obtained from birth certificates. Research staff measured children's length/height, weight, and waist circumference at 6 m (infancy), 3 y (early childhood), 7 y (mid-childhood), 12-13 y (early teen), and 14-15 (mid-teen)^{37,45}. Additional data on child weight and length/height were obtained from medical records at well-child visits. In IFPS II, mothers reported infant birth weight and length in neonatal survey; weight, length, and age at their most recent doctor's visit in 3-m, 5-m, and 7-m, 12-m, and 6-y surveys^{38,42}. Body mass index (BMI) was calculated as, weight in kg/(height in meters)². We will define stunting as height-for-age z score < -2, and underweight as sex- and age-specific BMI < 5th percentile according to World Health Organization (WHO) Growth Standards^{46,47}.

Obesity. In both Project Viva and IFPS II, we will define child obesity as sex- and age-specific BMI \geq 95th percentile according to WHO Growth Standards^{46,47}. In Project Viva, skinfold thickness was measured at 3 y, 7 y, 12-13 y, and 14-15 y. In addition, fat, lean and trunk fat mass were measured through whole-body dual X-ray absorptiometry (DXA) scans performed at 7 y, 12-13 y, and 14-15 y. Accordingly, we will calculate fat mass index (FMI, kg/m²), lean mass index (LMI, kg/m²), and trunk fat mass index (TFMI, kg/m²).

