Cardio-metabolic health. At the 7-y and 12-13-y visits in Project Viva, the child's systolic (SBP) and diastolic blood pressure (DBP) were measured with automated oscillometric monitors. In addition, the child's fasting blood was used to measure plasma glucose, insulin, adiponectin, and C-reactive protein (CRP), serum total cholesterol (TC), triglycerides (TG), and HDL⁴⁸. We will calculate LDL as, total cholesterol – HDL – (triglycerides/5). We will estimate insulin resistance through the homeostatic model assessment of insulin resistance (HOMA-IR = [glucose mg/dL \times insulin μ IU/mL]/405). A metabolic syndrome z score was derived by calculating the mean of five age- and sex-specific internal z scores for waist circumference, SBP, inverted HDL, natural log-transformed TG, and natural log-transformed HOMA-IR⁴⁸.

Risk of food allergy. In Project Viva, mothers reported the child's food allergy annually from 2 y to 11 y, at 12-13-y and 14-15-y of child age through the questions, - "In the past month, has your child avoided any foods because of a food allergy, intolerance, or sensitivity?", and "If yes, please specify". More details on food allergy were reported at the 7-y and 12-13-y visits using the question, - "Has your child ever had an allergic reaction to fish, shellfish, sesame seeds, peanuts or tree nuts?". In addition, at the 7-y and 12-13-y visits, food allergen sensitization of the child was defined as any serum specific IgE level of 0.35 IU/mL or greater to one of the food allergens listed, i.e., egg white, milk, wheat, peanut, and soybean⁴⁹. In the IFPS II, mothers reported whether their infant had food allergy in the past 2 weeks at 2-12 m of infant ages. Additional information on infant food allergy was collected at 4, 9, and 12 m:

whether food allergy (e.g., allergic reaction, sensitivity, or intolerance) happened at the first time of eating, exposure pathway, initial age, allergic symptoms, doctor visit, methods for testing food allergy, diagnosis, treatments, and food allergens including eggs. At the 6-y follow-up, mothers reported the child's status and history of food allergy, initial age, symptoms, testing methods, diagnosis, treatments, outgrowing food allergy, and food avoidance.

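### The lowest-risk 'infant' egg frequency would rest on Project Viva intake at about 2 years, reported at a wave when some children may already be avoiding egg for allergy

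*Combined protocol and SAP*

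**What the plan says.** **Hypothesis** (2) Research Project Objectives and Hypotheses). Hypothesis 3 reads: "We also predict a non-linear association between frequency of infant egg intake and the average probability of multiple child outcomes", with the best frequency expected at 2-4 times per week.

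**Average** (3) Project Design, Data analysis). The average gives equal weight to six binary outcomes: stunting, underweight, obesity, high metabolic syndrome risk, food allergy and cognitive delay. The lowest-risk consumption is the level at which this average is smallest.

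**Viva exposure** (Frequency of egg intake). At the 2-y survey "the frequency of infant egg intake in the past month was obtained from" the mothers' answer to an item on "how often your child eats each of the foods listed, on average, in the past month". The item was repeated at 3 y and 7 y.

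**IFPS II exposure** (Sample/Data; Frequency of egg intake). Egg feedings in the past 7 days were reported in surveys from 2 to 12 m, which the plan calls infant ages. The list of follow-up ages ends "10 m, 12 m, and 6 y of child age".

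**Allergy reports** (Risk of food allergy). In Viva, "mothers reported the child's food allergy annually from 2 y to 11 y", through an item on foods avoided in the past month because of allergy, intolerance or sensitivity, with a request to specify the food.

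**Adjustment** (Confounders). The list covers family, parental, maternal and early-feeding variables, including family health history. It does not list the child's own early allergy.

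**The concern.** Two things are at stake.

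The first is the age to which the conclusion applies. The conceptual framework leads from infant egg consumption to clinical guidelines. A lowest-risk frequency described as infant intake would be read as advice about the first year, when the data behind it describe children of about 2 years.

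The second is reverse causation. By 2 y a child may already be avoiding egg because of an allergic reaction. That child's low intake is then a result of allergy, not a possible cause of it. If the allergy lasts into mid-childhood, the same child can appear as a food-allergy case in the outcome. Infrequent intake could then look harmful for allergy even if frequency had no effect. The plan neither adjusts for early child allergy nor includes a sensitivity analysis on the point.

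**Working it through.** The plan gives no figure to reproduce here. The check compares what each cohort measured and when, then works out the direction of the possible bias.

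**1. Which cohort has the six outcomes** (Physical growth; Obesity; Cardio-metabolic health; Risk of food allergy; Cognition development)

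| Outcome | Viva | IFPS II |
|---|---|---|
| Stunting | yes | yes |
| Underweight | yes | yes |
| Obesity | yes | yes |
| Food allergy | yes | yes |
| Metabolic syndrome risk | yes | not described |
| Cognitive delay | yes | not described |

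Viva has 6 of 6 and IFPS II has 6 − 2 = 4 of 6. The multiple imputation paragraph covers missing outcomes, but it describes neither pooling the cohorts nor imputing outcomes that a cohort never measured. The six-outcome average is therefore a Viva result.

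**2. When frequency was measured**

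- Viva, earliest item: past month at 24 m, so about 23-24 m of age.
- IFPS II, last infant survey: 12 m.
- Gap: 23 − 12 = 11 to 24 − 12 = 12 months.

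Using Viva's 3-y or 7-y item would move the exposure further from infancy. The Background's 1,000-day window runs to the end of the second year, so 23-24 m lies inside it. It lies outside the 2-12 m that the plan calls infant ages. The Physical growth paragraph labels measurement visits "6 m (infancy), 3 y (early childhood), 7 y (mid-childhood" and later; that scheme gives 2 y no label. No cohort pairs first-year frequency with all six outcomes.

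**3. Direction of the possible bias in Viva**

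Suppose egg frequency has no effect on food allergy. Let *a* be the share of the 'never' class who avoid egg because of allergy at 2 y, *s* the probability that such a child counts as a later food-allergy case, and *r* the probability for every other child. Suppose also that all such avoiders are in 'never'. For a class-by-class fit:

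- Food-allergy probability in 'never' = *a·s* + (1 − *a*)·*r* = *r* + *a*·(*s* − *r*)
- Food-allergy probability in the other classes = *r*
- Excess in 'never' = *a*·(*s* − *r*), which is positive whenever *a* > 0 and *s* > *r*
- Excess in the equal-weight average of six = *a*·(*s* − *r*)/6, other outcomes unchanged

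A smooth fitted curve would spread the excess over neighbouring low frequencies. The documents give none of *a*, *s* or *r*, so no number can be put on it.

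Whether *s* exceeds *r* depends on persistence and on the outcome definition, which the plan leaves open for food allergy. The avoidance item can capture egg, and the IgE panel includes egg white. The item on ever having had a reaction, asked at 7 y and 12-13 y, does not list egg.

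**The case against.** The strongest reply is that the plan hides nothing. It names the 2-y survey and quotes the item, it relies on an early-life window that includes 23-24 m, and it says the cohorts' outcome measures are complementary. All of this stands. A reader might infer that the exposure is invalid or its timing concealed; the documents do not support that. What remains is that the hypothesis and conclusion carry an age label that their only six-outcome source does not match.

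A reader might also infer that the average has no defined cohort. In fact the outcome descriptions imply Viva, and the frequency classes match Viva's response options. The hoped-for external replication is of findings generally, so outcome-by-outcome comparison on shared outcomes remains possible. The six-outcome limit also affects Hypothesis 2, but Viva asked about age at introduction at 6 m and 12 m, so the exposure-age mismatch is specific to Hypothesis 3.

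Nor is IFPS II shown to be unworkable. The plan reports that "1.7% and 63.0% of IFPS II infants had been introduced eggs by 6 m and 12 m of age". Applied to all 3,033, that is 0.017 × 3,033 ≈ 52 infants by 6 m, but 0.630 × 3,033 ≈ 1,911 by 12 m, and the plan never proposes 6 m as the exposure. The intake figures, "0.01 (SD, 0.10) and 0.27 (SD, 0.37) serving/week at 6 m and 12 m", do not establish sparse classes at 12 m either. If they were whole weekly feedings, the mean square could not be below the mean, yet 0.37² + 0.27² = 0.210 < 0.27. The stated unit therefore cannot be read as whole feedings per week.

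On reverse causation, the reply is that outcomes are assessed in mid-childhood and adolescence, so carry-over needs persistence, and that food allergy is one of six outcomes. Both points limit the claim to direction. Exclusion also has a cost: it removes true allergy cases, mostly from 'never', and avoidance at 2 y may itself reflect earlier feeding. It therefore belongs in a sensitivity analysis and should not replace the main one.

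**Conclusion.** The point holds in two parts. First, the six-outcome lowest-risk frequency can come only from Viva as described, and so concerns intake at about 2 y, 11-12 months beyond the last IFPS II infant survey. This follows directly from the text.

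Second, egg frequency and avoidance because of allergy are reported at the same wave, so predicted food allergy at the low-frequency end can be biased upward. This assumes that some children avoid egg because of allergy at 2 y, that they are mostly classed as 'never', that the allergy persists, and that the outcome definition captures egg. Only the direction is claimed. A reader might infer that the identified optimum is wrong or would move, but nothing in the documents shows that.

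The planned analysis remains usable. Its label should be corrected and its sensitivity to early egg avoidance reported.

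**What to change.** 1. Label the Viva exposure as egg intake frequency at 2 y. Restate Hypothesis 3 and the lowest-risk conclusion for that age. State that the six-outcome average is a Viva-only result that IFPS II cannot replicate.
2. Keep the planned Viva Aim 2 analysis as the main one. Add a sensitivity analysis of the models and the average probability that excludes children reported at the 2-y wave as avoiding egg, identified from the specified-food answer. Use the same population for all six outcomes, and give the number excluded in each frequency class. Report both versions and discuss any difference at 'never' or in the optimum, without a binding decision rule.
3. Optional clarifications: name the IFPS II frequency measure (one survey month or a summary over 2-12 m), and add a labelled four-outcome comparison across cohorts, noting the different exposure ages.

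The cost is wording and one repeated analysis on existing data. The downsides are a narrower claim about infancy, slightly fewer children in the repeated analysis, and the loss of some true allergy cases that may reflect earlier feeding. The two versions should therefore be read together.

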Cognition development. In Project Viva, the child's cognition development, including intelligence, visual-motor, and memory-learning, was measured at 3 y and 7 y of age⁵⁰. For the intelligence domain, trained research staff administered the Peabody Picture Vocabulary Test-3rd edition (PPVT-III, a test of receptive language) at 3 y of age, and the Kaufman Brief Intelligence Test-2nd edition (KBIT-II, verbal and non-verbal intelligence) at 7 y of age. For the visual-motor domain, research staff administered the Wide Range Assessment of Visual Motor Abilities (WRAVMA) at the 3-y visit. WRAVMA includes the fine motor (pegboard), visual spatial (matching), and visual motor (drawing) subtests. Subtest scores were combined to yield the total WRAVMA score. At the 7-y visit, staff administered the WRAVMA visual motor (drawing) subtest only. For the memory-learning domain, staff administered the design memory and picture memory subsets of Wide Range Assessment of Memory and Learning (WRAML) at the 7-y visit. These two subset scores were combined to yield the total WRAML score.

Effect modifier. We are interested in effect modification by child sex (Boys vs Girls).

Confounders. Potential confounders include family income; health history of family members; parental education attainment, employment, and preconception BMI; and maternal intelligence, age, race/ethnicity, marital status, parity, pregnancy complications, prenatal vitamins, smoking, and delivery method; early mode of infant feeding including breastfeeding duration and exclusivity. We will also adjust for child actual age at assessments.

Data analysis. All our analyses will be first conducted among boys and girls separately to examine the potential sex differences (if significant, sex-stratified results will be reported).

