For **Aim 1 (infant age of egg introduction)**, we will first classify the infants based on their age of egg introduction: never, <2 m, 2-3 m, 4-5 m, 6-8 m, 9-11 m, and 12 m. Then we will compare their physical growth, obesity, cardio-metabolic risk profile, risk of food allergy, and cognition test scores in mid-childhood and adolescence using Chi-square tests (categorical outcomes) or ANOVA tests (continuous outcomes). We will fit multivariable linear (continuous outcomes) or logistic (binary outcomes) regression models with fractional polynomial functions of infant age of egg introduction, adjusted for significant confounders. Both linear (e.g., earlier introduction, high probability of the outcome) and non-linear (e.g., threshold effect) associations will be tested. The non-linear trend will be examined through visualization of scatter plots and statistical tests of polynomial term of infant age of egg introduction in the regression models. If the polynomial terms of age are not significant, we will drop it and consider the association to be linear.

Then, we will fit a mixed effect model (SAS PROC MIXED) for continuous outcomes (height z-score and BMI z-score) and a generalized linear mixed effect model (SAS PROC GLIMMIX) for binary outcomes (obesity and diagnosis of food allergy) that were measured repeatedly across multiple age points. The mixed effect model will include random intercepts, random slopes for age effects, and autoregressive variance-covariance matrix across different time points. Independent variables in the model will include infant age of egg introduction, outcome age point (mid-childhood and adolescence), the 2-way interaction term (infant age of

egg introduction × outcome age point), and significant covariates. The 2-way interaction term quantifies the extent to which infant age of egg introduction can affect the specific outcome. The PI has experience with using mixed effect models for examine child growth measures and multiple publications in this area.^{51,52}

For **Aim 2 (frequency of infant egg intake)**, we will first classify the infants based on their frequency of egg intake: never, <once/week, once/week, 2–4 times/week, nearly daily or daily, and ≥ 2 times/day. Then, we will use similar analytic methods mentioned above for Aim 1 to compare their health and developmental outcomes.

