In addition, we will create an **average probability of multiple child outcomes** to balance across different aspects of child health and development using the methods published by Oken et al.⁵³ for identifying the lowest-risk exposure level when multiple outcomes are considered. Specifically, we will focus on 6 binary child outcomes including stunting, underweight, obesity, high risk of metabolic syndrome (e.g., z score $\geq 95^{\text{th}}$ percentile), food allergy, and cognitive delay (e.g., standardized cognition score < 85 points). We will use estimates from aforementioned logistic models to generate predicted probabilities of each of the 6 adverse outcomes when the independent variable of infant egg consumption (i.e., age of egg introduction or frequency of egg intake) varies across the observed range within our study sample. We will calculate the average probability of the 6 outcomes, assuming these outcomes are equally important. We will identify the lowest-risk infant egg consumption when the corresponding average probability of the 6 adverse outcomes is the lowest.

We will handle missing data with Multiple Imputation.⁵⁴ Specifically, we will first generate 20 replicates of datasets (PROC MI in SAS) with imputed values for missing data on infant egg consumption, child outcomes, and significant covariates, based on a bayesian approach. The 2nd stage is to use standard statistical methods (e.g., Linear Regression) to fit the model of interest to examine the association between infant egg consumption and the specific outcome within each of the 20 imputed datasets. The 3rd stage is to pool the analytic results from all 20 imputed datasets to get the average estimates of the association (PROC MIANALYZE). The PI has experience with Multiple Imputation for large datasets.⁵⁵

All our analyses will be first conducted among boys and girls separately to examine the potential sex differences. A formal interaction test will be conducted by including the interaction term of egg consumption and sex into the regression models. If the interaction term is significant, sex-stratified results will be reported. Otherwise, sex-pooled analytic results will be reported.

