Statistical Power. We expect sufficient statistical power for our hypothesis-driven data analyses for both Aims, because 1) the 2 cohorts had relatively large sample sizes (N=2,128 for Project Viva and N=3,033 for IFPS II), which are sufficient to detect a small odds ratio (1.46 for Project Viva, 1.38 for IFPS II with type 1 error being 0.05 and power being 0.8) of binary child outcomes (e.g., food allergy) between infants with different egg consumption (e.g., egg introduced at ≥ 12 m vs 6-8 m) or a small effect (effect size=0.054 for Project Viva, 0.051 for IFPS II) of infant egg consumption on continuous outcomes (e.g., intelligence score); 2) most child outcomes were measured repeatedly; 3) infant egg consumption varied largely within cohorts.

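### Parental height is missing from the candidate confounders although child height z-score and stunting are outcomes; adding it where recorded is a cheap, minor improvement, mainly in precision

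*Combined protocol and SAP*

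**What the plan says.** All references are to section 3, Project Design, of the combined protocol and SAP.

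- **Child outcome measures, Physical growth:** "We will define stunting as height-for-age z score < -2". The same paragraph gives the BMI formula used for the children: "Body mass index (BMI) was calculated as, weight in kg/(height in meters)²".
- **Data analysis, Aim 1:** the mixed models cover "continuous outcomes (height z-score and BMI z-score", and the term of interest is the interaction of age at egg introduction with outcome age point. The regression models are "adjusted for significant confounders"; no criterion for significance is given.
- **Average probability of multiple child outcomes:** the index averages "6 binary child outcomes including stunting, underweight, obesity" and three others, with equal weight.
- **Confounders:** the list opens "Potential confounders include family income; health history of family members" and continues with "parental education attainment, employment, and preconception BMI", then maternal and infant-feeding variables.

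Parental height appears nowhere; every mention of height concerns the child. The documents do not say whether either dataset holds parental height.

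**The concern.** Parental stature is an obvious familial predictor of child height. It is fixed before egg introduction and cannot be changed by it, so adjusting for it does not remove any effect of eggs. The list carries a familial counterpart for other outcomes: parental BMI for obesity, maternal intelligence for cognition, and family health history for allergy and cardio-metabolic risk. Height has none.

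BMI does not fill the gap, because dividing weight by height squared largely removes stature. A model that adjusts for parental BMI but not parental height therefore leaves familial variation in stature in the error term. If parental height also differed by feeding practice after the listed covariates, part of an egg-height association could be familial.

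**Working it through.** **1. The plan's own figure.** Statistical Power quotes detectable effects of 0.054 and 0.051 on continuous outcomes, with "N=2,128 for Project Viva and N=3,033 for IFPS II", type 1 error 0.05 and power 0.8. The metric is not stated. Read as a standardised slope, the minimum is (z_alpha + z_power)/√N:

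| Cohort | Two-sided | One-sided | Stated |
|---|---|---|---|
| Project Viva, N = 2,128 | 2.80/√2,128 = 0.0607 | 0.0539 | 0.054 |
| IFPS II, N = 3,033 | 2.80/√3,033 = 0.0509 | 0.0451 | 0.051 |

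No single convention gives both stated values. That is a separate matter. The two-sided values serve as the baseline below.

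**2. How much of parental height BMI captures.** The share is the squared correlation. For an assumed parental BMI-height correlation of 0 to −0.3, it is 0 to 9%.

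**3. Precision in the linear height z-score models.** Let r be the partial correlation of parental height with child height z-score given the listed covariates. The range 0.3 to 0.6 is an assumption. For a covariate unrelated to exposure, residual variance is multiplied by 1 − r², the sample-size equivalent is 1/(1 − r²), the detectable slope is multiplied by √(1 − r²), and an effect with 80% power has power Φ(2.80/√(1 − r²) − 1.96) after adjustment.

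| r | Variance reduction | Sample-size equivalent | Power | Detectable slope, Viva | Detectable slope, IFPS II |
|---|---|---|---|---|---|
| 0.3 | 9% | 1.10 | 84% | 0.0579 | 0.0485 |
| 0.4 | 16% | 1.19 | 86% | 0.0557 | 0.0466 |
| 0.5 | 25% | 1.33 | 90% | 0.0526 | 0.0441 |
| 0.6 | 36% | 1.56 | 94% | 0.0486 | 0.0407 |

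The slopes use full enrolment; the percentages do not depend on N. IFPS II heights are mother-reported, and that measurement error would push r towards the lower end.

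**4. The mixed-model interaction.** For child i at visit t, write Y_it = a_t + b_t·E_i + g·H_i + u_i + e_it, where E is age at egg introduction and H parental height with a constant effect g. The within-child difference is Y_i2 − Y_i1 = (a_2 − a_1) + (b_2 − b_1)·E_i + (e_i2 − e_i1). Both g·H_i and u_i drop out. The interaction b_2 − b_1 is thus neither biased by omitting H nor sharpened by adding it. A simulation of 1,000 children with two complete visits, and a 0.10 correlation between H and E, gave the same interaction estimate and practically the same standard error with and without H. With missed visits the cancellation is approximate. If the familial effect changes with age, a main-effect covariate does not deal with it.

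**5. Stunting.** A logistic model has no residual variance to reduce. Omitting a strong predictor pulls the conditional odds ratio towards 1 and costs some power. At the growth-reference rate P(z < −2) = 2.3% (an assumption for these cohorts), expected events are 0.02275 × 2,128 ≈ 48 and 0.02275 × 3,033 ≈ 69, about half of that per sex in the planned sex-separate analyses.

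**The case against.** The strongest case against has four parts.

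- **The list is open.** It is worded as potential confounders, shared across outcomes, and only significant ones are kept. So it is too strong to say that the height models are fixed as adjusted for parental BMI. This stands. Still, parental height is not a named candidate, and the imputation covers only egg consumption, outcomes and significant covariates, so nothing in the text brings it in.
- **The interaction is the stated target of the mixed models.** There a constant familial effect cancels, as shown above. This stands and limits the benefit to the exposure main effect.
- **Availability is inferred.** BMI normally requires height, but the formula in the plan is for the children, and a secondary dataset may hold parental BMI only as a derived variable. This stands, so the request must be conditional.
- **Stunting is sparse.** One or two more forced parameters are not free with 48 to 69 expected events. This also stands.

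A reader might go further and infer that the height and stunting results will be confounded and true nulls often rejected. Multiplying an assumed correlation of 0.05 to 0.10 between parental height and egg timing by an assumed 0.4 to 0.6 with child height does give a spurious standardised slope of 0.02 to 0.06, a range that includes the plan's stated detectable effects. But nothing in the documents links parental height to egg timing, and the likely routes (race/ethnicity, income, education) are already candidates. Those figures are purely illustrative; false-rejection rates built on them should not be quoted as findings.

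**Conclusion.** The omission is real and the point stands as a cheap, minor improvement. It rests on three things: parental height is absent from the candidate list, BMI is a poor proxy for stature, and height z-score and stunting are both analysed. The benefit is mainly precision for the exposure main effect in the linear height z-score models: 80% power becomes 84 to 94% if the assumed partial correlation of 0.3 to 0.6 holds. These figures do not carry over to the mixed-model interaction or to the logistic stunting models. Residual confounding by parental height remains possible and is not demonstrated.

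**What to change.** - Where parental height is recorded, pre-specify maternal height, and paternal or mid-parental height where available, as a covariate in the height z-score models, exempt from the significance screen.
- Include it in the multiple imputation model.
- In the stunting models, use it as far as the number of events allows; a single maternal or mid-parental term is the economical choice.
- If a cohort does not hold parental height, state that as a limitation of its height and stunting results.

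The cost is one or two covariates and a line or two of text, with no new data collection if the heights are on file. The downsides are missing or proxy-reported paternal height, which would lean on the imputation, and one or two more parameters in stunting models with few events.
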